### 8.3.2 Efficacy Endpoints

#### 8.3.2.1 Primary Endpoint

The primary efficacy endpoint is the CAPS-5 total severity score change from baseline as compared to placebo. Mean change from baseline compared with placebo in CAPS-5 total severity score using MMRM.

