### 2.4.1 Completed Open-Label Study in PTSD Patients (IMPACT-1 Part A)

Part A of this study, completed in the UK, was an open-label evaluation of the safety, tolerability, and efficacy of methylone in adults with severe PTSD (CAPS-5  $\geq 35$ ; Jones 2023). Fourteen (14) participants were treated with open-label methylone once a week for 4 weeks (4 treatment sessions). During each treatment session, participants received an initial dose of 150 mg methylone followed by 100 mg of methylone 90 minutes later. Following the Treatment Period, participants entered a 6-week Follow-up Period and a final study visit at Week 10. The primary efficacy endpoint was the change from baseline on the CAPS-5 total severity score. At baseline, the mean CAPS-5 score was 47.8 points.

Treatment with methylone resulted in rapid, robust, and durable effects. Two days after the first dose, the mean change from baseline in CAPS-5 total severity score was -8.4 points. Methylone provided robust improvements in CAPS-5, with the mean change from baseline of -23.3 points two days after the 2nd dose. Six weeks after the last dose, the results were durable with a mean change from baseline in CAPS-5 of -36.2 points. Remission, defined as a CAPS-5 total score of  $\leq 11$ , was achieved by the majority of participants (61.5%) at the end of study.

Methylone was well tolerated with no drug-related or treatment-emergent serious adverse events to date. The most commonly occurring treatment-emergent adverse event (TEAE) was headache (43%), followed by decreased appetite (29%), non-cardiac chest pain (21%), and fatigue (21%). One unrelated serious adverse event of 'victim of assault' occurred after a participant was off study drug for 20 days.

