**Table 2: Objectives and Endpoints for Part B**

Objectives	Endpoints
Primary	
To assess the efficacy of methylone in treating PTSD symptoms.	Mean change from baseline to Week 10 compared with placebo in CAPS-5 total severity score.
Secondary	
To assess the effect of methylone compared to placebo on sleep quality, functional disability, treatment satisfaction, quality of life, and physical function in participants with PTSD.	
Mean change from baseline compared with placebo in the following scales:
 
 
• CGI-S
 
• MADRS
 
• SDS
 
• PCL-5
 
• PGI-S
 
• BDI-II
 
• WEMWBS
 
• PSQI
 
 
Percentage of participants with:
 
 
• Treatment response, defined as a 
 
○ <math>\geq 10</math> point reduction on the CAPS-5 from baseline
 
○ 30% improvement from baseline on CAPS-5
 
○ 50% improvement from baseline on CAPS-5
 
 
 
• Remission, defined as a score of <math>\leq 11</math> on the CAPS-5
 
• Improvement on the PGI-C
 
• Improvement on the CGI-I
 

To assess the safety and tolerability of oral methylone compared to placebo administered weekly over 4 weeks in participants with PTSD.	
 
• Incidence and severity of TEAEs
 
• Incidence and severity of AESIs
 
• Change in HR, SBP, DBP and temperature during each dosing session
 
• Clinically significant changes in ECG
 
• Changes from baseline in clinical laboratory parameters (clinical chemistry, hematology, and urinalysis)
 

[REDACTED]	
Effect of the following scales, compared with placebo:
 
 
• PTGI
 
• [REDACTED]
 
• [REDACTED]
 

Abbreviations: [REDACTED] AE = adverse event; AESI = adverse event of special interest; BDI-II = Beck Depression Inventory-II; DBP = diastolic blood pressure; CAPS-5 = Clinician-Administered PTSD Scale for DSM-5; CGI-I = Clinician Global Impression of Improvement; CGI-S = Clinical Global Impression of Severity; C-SSRS = Columbia Suicide Severity Rating Scale; DBP = diastolic blood pressure; ECG = electrocardiogram; HR = heart rate; LEC-5 = Life Events Checklist for DSM-5; MADRS = Montgomery-Åsberg Depression Rating Scale; [REDACTED] MINI = Mini International Neuropsychiatric Interview; PCL-5 = PTSD

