### 9.5.2 **Efficacy Statistical Analysis**

The primary efficacy endpoint is the CAPS-5 total score change from baseline to Week 10 as compared to placebo.

All efficacy endpoint data will be listed for individual participants. All continuous efficacy endpoints will also be summarized by descriptive statistics (n, arithmetic mean, SD, median, minimum and maximum) by study part, overall, by treatment (for Part B) and study period. All categorical efficacy endpoints will be summarized by descriptive statistics (n, percentage).

For Part A the change from baseline to each timepoint will be presented along with a paired *t*-test p-value.

A Mixed Model for Repeated Measures (MMRM) will be fitted for select efficacy endpoints to analyze the difference between treatments for Part B. The model will include treatment, visit, and treatment by visit interaction as fixed effects, where visit is the repeated effect. The baseline value will be included (if applicable) as a covariate. All tests will be based on two-sided significant level of 0.05. Full details of the statistical analysis for each endpoint will be described in the SAP.

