## 1 INTRODUCTION

This statistical analysis plan (SAP) is based on the protocol TT-TSND-201 of Transcend Therapeutics, ‘A Pilot Study to Assess the Use of Methylone in the Treatment of PTSD IMPACT-1 (Investigation of Methylone for Post-Traumatic Stress Disorder [PTSD])’. This SAP is used for Part B of protocol TT-TSND-201.

The purpose of this SAP is to outline in detail the statistical methods, data derivations, method for handling missing data, definition of analysis population and presentations of data. Specifications for tables, figures, and listings are contained in a separate document. Unless otherwise stated with reasoning, the methods discussed in this SAP are the ones outlined in the Protocol.

This SAP is written in compliance with the ICH E3 (Structure and Content of Clinical Study Reports) and ICH E9 (Statistical Principles for Clinical Trials) published by the International Coordination of Technical Requirements for the Registration of Human Drugs (ICH).

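### Does SAP 8.3.2.1 leave the Part B primary endpoint open by leaving out Week 10?

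*SAP*

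**What the plan says.** The protocol gives the Part B primary endpoint a timepoint each time it states it. Table 2, which repeats the synopsis, has "Mean change from baseline to Week 10 compared with placebo in CAPS-5 total severity score". Section 9.5.2 has "The primary efficacy endpoint is the CAPS-5 total score change from baseline to Week 10 as compared to placebo".

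SAP 8.3.2.1 follows the Section 9.5.2 sentence closely but drops the timepoint: "The primary efficacy endpoint is the CAPS-5 total severity score change from baseline as compared to placebo". It then says only that the comparison uses the MMRM. SAP 8.3.1.1 puts treatment, visit and their interaction in that model and plans a methylone-placebo contrast at every visit. The sample code in SAP Appendix 3 requests least-squares mean differences for treatment averaged over visits and for treatment by visit. Neither place marks one contrast as primary.

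Two other parts of the SAP bear on the reading. Section 1 states: "Unless otherwise stated with reasoning, the methods discussed in this SAP are the ones outlined in the Protocol". Section 9.1 lists seven changes from the protocol, and none concerns the timepoint of the primary endpoint.

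**The concern.** A primary endpoint is fully specified only when the measure, the comparison and the timepoint are all fixed. Someone reading the SAP alone would find the first two and not the third. The model would give that reader several treatment differences, SAP 8.1.5 applies no multiplicity adjustment, and SAP 8.1.6 tests at one-sided 0.05. If the primary contrast could be settled after unblinding, the nominal level would no longer describe the chance of a false positive claim.

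The choice could also change the estimate. In Part A, Protocol 2.4.1 reports "Two days after the first dose, the mean change from baseline in CAPS-5 total severity score was -8.4 points", then a "mean change from baseline of -23.3 points two days after the" second dose, and finally "Six weeks after the last dose, the results were durable with a mean change from baseline in CAPS-5 of -36.2 points". A difference averaged over all visits would mix early, small changes with late, large ones. It would answer a different question from a difference at the last visit.

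**Working it through.** **Which visit is Week 10?** On Part A, whose schedule Part B shares, Protocol 2.4.1 says: "Following the Treatment Period, participants entered a 6-week Follow-up Period and a final study visit at Week 10". Protocol 4.6.1 puts the last visit at Day 64. The design schema, printed in both documents, shows a 4-week treatment period and a 6-week follow-up ending on Day 64.

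- Treatment plus follow-up: 4 + 6 = 10 weeks.
- From the last dose (Day 22) to Day 64: (64 - 22)/7 = 6.0 weeks.
- From Day 1 to Day 64: (64 - 1)/7 = 9.0 weeks, so Day 64 is the first day of the tenth week.

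The Schedule of Assessments places the past-week CAPS-5 after baseline on Days 3, 10, 17, 24, 29, 36, 43 and 64, plus early termination. The visit before the last has a window of Day 43 ± 2 (latest Day 45), and the last has Day 64 ± 3 (earliest Day 61). The windows do not meet, so no second visit competes for the label.

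**What does the planned analysis produce?** With eight scheduled visits and two arms, and early termination not treated as a separate visit level, there are 8 same-visit treatment contrasts. The sample code adds 1 visit-averaged treatment difference, making 9. The code also prints comparisons across visits, which SAP 8.3.1.1 does not plan to use. The Day 64 contrast is one of the 8, so the model already supplies the estimate the protocol asks for.

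**What would a free choice cost?** The documents give no between-visit correlations, so these are assumed. Simulated null contrasts at one-sided 0.05 gave the following chance of at least one false positive among the 9:

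| Assumed correlation | Chance |
|---|---|
| Exchangeable, 0.9 to 0.3 | about 0.11 to 0.27 |
| First-order autoregressive, 0.9 to 0.6 | about 0.15 to 0.25 |
| Day 64 fixed as primary | 0.05 |

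**How far might the averaged contrast differ?** The Part A changes at Days 3 and 10 are 8.4/36.2 = 23% and 23.3/36.2 = 64% of the final change. Suppose the treatment difference followed that profile, with straight lines between the three reported points, and equalled the planning value of 11 at Day 64. The eight shares are then 0.23, 0.64, 0.69, 0.74, 0.77, 0.82, 0.86 and 1.00, with mean 0.72, and the averaged difference is about 7.9 points. This is an illustration only. The inputs are uncontrolled within-arm means, and five of the eight visits are interpolated.

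**Does the sample size depend on it?** No. With a difference of 11, SD 12 and two-sided 0.05, a t-test needs 19.7, so 20 per arm, for 80% power and 26.01, so 27 per arm, for 90%, as stated. Then 27/0.85 = 31.8, so 32 per arm and 64 in total. The visit does not enter the formula.

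**The case for a change.** The strongest opposing case is that Week 10 is reached by inference. Protocol 9.3 sends the reader to the final SAP for the final analysis methods, and no SAP sentence names a primary visit. SAP Section 1 speaks of methods, which need not cover endpoint definitions. Silence in SAP 9.1 is not proof either, because that list is incomplete. Vital signs are seated in Protocol 7.3 and supine in SAP 6.2.3, and the C-SSRS summaries differ between Protocol 9.5.1.6 and SAP 8.4.6; neither difference is listed. The sample-size text also refers to an effect at the end of treatment.

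The facts in this case are correct, and the missing phrase is real. They do not open a choice. Protocol 9.3 lets the SAP settle methods; it does not say that the SAP may redefine the endpoints of Protocol Section 3. An omission also differs from a conflicting statement: nowhere does the SAP propose another visit or the average as primary. The end-of-treatment wording is the same in Protocol 9.2 and SAP Section 4 and describes the cited MDMA trial, so it sets no timepoint here. The by-visit CAPS-5 summaries placed under secondary endpoints contradict nothing in the protocol. The sample code is a generic template shared by all continuous endpoints, so the absence of a CAPS-5 label in it means little. The table shells are in a separate file that could not be checked and may already mark the primary row.

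**Conclusion.** The concern does not call for a change. The SAP omits a timepoint that the protocol states in three places, and an analyst working from both documents would report the Day 64 treatment difference as primary. On that reading the type I error is the nominal 0.05, one-sided under the SAP, and neither the model, the sample size nor the estimate moves. Writing the phrase into the SAP would record what is already fixed and alter no result.

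This rests on two assumptions: that the SAP is read with the protocol, as its Section 1 provides, and that the omission was not a deliberate but undeclared change of endpoint, of which the documents give no sign. The false-positive range of 0.11 to 0.27 and the averaged difference of 7.9 points describe an analysis that neither document proposes as primary.

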#### 8.3.2.2 Secondary Endpoint

##### 8.3.2.2.1 CAPS-5

The CAPS-5 total severity score (absolute, change from baseline) will also be summarized by visit.

Summary percentage of participants by visit having

- Treatment response, defined as:
  - $\geq 10$  point reduction on the CAPS-5 from baseline
  - $\geq 30\%$  improvement from baseline on CAPS-5
  - $\geq 50\%$  improvement from baseline on CAPS-5
- Remission, defined as:
  - A score of  $\leq 11$  on the CAPS-5

##### 8.3.2.2.2 MADRS

Mean change from baseline compared with placebo in MADRS total score using MMRM.

The MADRS total score (absolute, change from baseline) will also be summarized by visit.

Summary percentage of participants by visit having

- Treatment response, defined as:
  - $\geq 50\%$  improvement from baseline on the MADRS
- Remission, defined as:
  - A score of  $\leq 10$  on the MADRS

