#### 2.1.1 Post-Traumatic Stress Disorder

Post-traumatic stress disorder (PTSD) is a serious debilitating disorder that occurs in people who have experienced or witnessed a traumatic event such as a natural disaster, a serious accident, or who have been threatened with death, sexual violence, or serious injury. Current estimates suggest that 1 in 3 people that experience a traumatic event will be affected by PTSD, however there is no clear biomarker that explains why some people develop the condition and others do not (NHS 2023). Post-traumatic stress disorder has a point prevalence estimated at nearly 3% in the UK (McManus 2009). International studies of lifetime prevalence show considerable variations in rates between nations, however it is estimated that 6.8% of US adults and one in 11 people in the UK will be diagnosed with PTSD in their lifetime (McManus 2009, NIMH 2023, Greenberg 2015). Symptoms of PTSD include intrusive thoughts and memories, negative effects on cognition and mood, hyperarousal and reactivity, and avoidance that do not remit for at least 1 month subsequent to exposure to a traumatic event (Koenen 2017). Individuals with PTSD may experience a substantial reduction in quality of life and relationships, and the disability resulting from PTSD can have further negative consequences such as obesity, hypertension, comorbid mental health conditions, and suicidality (Scott 2008,

Kibler 2009, Dorrington 2014, Tarrier 2004). Approximately half of people diagnosed with PTSD also have a diagnosis of major depressive disorder (MDD) across a range of populations with varying health and social histories (Flory 2015, Kessler 1995, Peconga 2020, Stein 2001).

First-line pharmacological treatments for PTSD include selective serotonin reuptake inhibitor (SSRI) medications, and psychotherapy (Arroll 2005, Cipriani 2018, Forbes 2010, Hoskins 2015, Kato 2018, Stein 2006). Unfortunately, many people suffering from PTSD either do not receive treatment or are not responsive to existing treatments (Stein 2006). Thus, there is a substantial treatment gap for patients with PTSD, which creates considerable burdens on patients and healthcare systems.

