## 6.2 Exclusion Criteria

1. Participant has a primary diagnosis of any other DSM-5 disorder, as assessed by the MINI Version 7.0.2.
2. Participant has a body mass index (BMI)  $<18 \text{ kg/m}^2$  or  $\geq 40 \text{ kg/m}^2$ .
3. Participant is known (or meets DSM-5 criteria for moderate or severe substance use disorder [mild substance use disorder may be allowed, after consultation with the sponsor, if use of the substance is unlikely to confound the study results]) to abuse illegal drugs or has a positive urine test for illegal drugs at Screening, Baseline, or prior to dosing on Day 1. The Investigator must confirm the participant is not otherwise impaired prior to dosing on Day 1.
4. Known history of:
  - a. Hepatitis B,
  - b. Hepatitis C, or
  - c. Infection with human immunodeficiency virus.
5. Participant smokes an average of  $>10$  cigarettes and/or e-cigarettes per day.
6. Abnormal LFTs at Screening:
  - a. AST, ALT or gamma-glutamyl transferase (GGT)  $>2 \times$  the ULN.

- b. Total bilirubin levels  $>1.5 \times$  the ULN (participants with a diagnosis of Gilbert's syndrome with high unconjugated bilirubin are eligible provided they meet other LFT criteria).
7. Moderate to severe renal impairment at Screening, with an estimated glomerular filtration rate (eGFR) of  $\leq 80$  mL/min according to the Cockcroft-Gault equation.
8. Active suicidal ideation and/or intent within 2 months of Screening, indicated by a 'Yes' response to suicidal ideation question 4 or 5 on the C-SSRS.
9. Any history of suicidal behavior within the last 5 years (excluding suicidal ideation):
  - a. Medical history of suicide attempt, or
  - b. 'Yes' response to the following suicidal behavior questions on the C-SSRS:
    - i. actual attempt, or
    - ii. interrupted attempt, or
    - iii. aborted attempt.
10. Uncontrolled hypertension at Screening (after 5 minutes rest):
  - a. SBP  $>140$  mmHg, or
  - b. DBP  $>90$  mmHg.
11. Resting heart rate at Screening of  $\geq 90$  bpm (after 5 minutes rest).
12. Have any history, physical or psychological symptoms, medication or other relevant findings that would make a participant unsuitable for the study based on the clinical judgement of study personnel. This would include (but is not limited to):
  - a. A need to continue active psychotherapy or pharmacotherapy during the study period.

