## 5 ANALYSIS SETS

### 5.1 Modified Intent-to-Treat (mITT) Population

The mITT population includes all participants who are randomized, received at least 1 dose of study drug and have at least 1 valid post-baseline assessment. Participants are analyzed on the treatment to which they are randomized to receive.

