## 8.3 Efficacy Analysis

These analyses will be based on the mITT Population. All efficacy endpoint data will be listed for individual participants.

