#### 8.3.1.2 Analyses for Categorical Efficacy End Points

Frequency tables and the Cochran–Mantel–Haenszel (CMH) test will be applied to the actual value of each visit. The descriptive statistics (n and percentage) for the treatment arms, and difference between treatment arms as well as the two-sided confidence interval of the treatment difference will be presented. The confidence interval will be constructed based on normal approximation.

See [Appendix 3 MMRM and CMH SAS Sample Code](#).

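### MADRS remission and response have no baseline floor, so a participant who starts and stays at 10 or below is counted as a remitter without changing

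*SAP*

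**What the plan says.** SAP 8.3.2.2.2 introduces both MADRS measures with "Summary percentage of participants by visit having". Response is at least 50% "improvement from baseline on the MADRS" and remission is a score of 10 or below. It sets no minimum baseline score and names no subset. SAP 8.3 says of the efficacy analyses: "These analyses will be based on the mITT Population". That population (SAP 5.1) consists of randomized participants who "received at least 1 dose of study drug and have at least 1 valid post-baseline assessment", with no condition on depression. SAP 9.1 lists the extra MADRS derivations as additions to the protocol.

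Entry severity is set on the CAPS-5 alone: 35 or more at Screening and 28 or more at Baseline (Protocol 6.1, criterion 3). No MADRS or BDI-II threshold appears. The exclusion that bears on depression is "Participant has a primary diagnosis of any other DSM-5 disorder, as assessed by the MINI Version 7.0.2" (Protocol 6.2, criterion 1), so comorbid depression is allowed but not required. Protocol 2.1.1 puts major depression at around half of people with PTSD. The MADRS runs from 0 to 60 (SAP 6.1.2).

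For categorical efficacy endpoints in general, SAP 8.3.1.2 says the CMH "test will be applied to the actual value of each visit". The sample code in SAP 11.3 has no stratum for the baseline score.

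**The concern.** Remission should mean that someone who was ill no longer is. Under this definition a participant at 8 at baseline and 8 at every visit is in remission from Day 3 onward. The remission percentage can then mix people who recovered with people who never had depressive symptoms above the cut-off.

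The CAPS-5 remission rule in SAP 8.3.2.2.1 has the same form but is protected by the entry criteria. With a Baseline score of at least 28 and a cut-off of 11, nobody reaches it without falling at least 17 points. The MADRS rule was added without an equivalent safeguard.

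The rates may be carried forward. SAP 8.1.5 says the findings will be used to design and power later trials, and SAP 9 foresees submissions and manuscripts. A remission rate that is too high in both arms, with a difference that is too small, is a poor basis for either use.

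**Working it through.** The plan states no expected MADRS response or remission rate, so there is no figure of its own to reproduce. What can be checked is what the definition does.

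**Inputs from the documents.** Cut-off 10 or below, no baseline floor (SAP 8.3.2.2.2). One-sided 0.05 (SAP 8.1.6). Evaluable participants per arm: 27. Randomized per arm: 32, since 27/0.85 = 31.8 (SAP 4).

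**Assumptions, not in the documents.** A share q of each arm starts and stays at 10 or below, with q from 0 to 30%. Among the others, remission p is 50% on methylone and 25% on placebo.

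**Rates as the SAP is written.** Reported remission = q + (1 − q)p in each arm, so each rate rises by q(1 − p) and the difference is (1 − q)(p_methylone − p_placebo). At q = 0.2: 0.2 + 0.8 × 0.50 = 0.60; 0.2 + 0.8 × 0.25 = 0.40; difference 0.8 × 0.25 = 0.20.

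| q | Methylone | Placebo | Difference (points) | SE of difference, 32 per arm (points) | Power, all mITT | Power, baseline above 10 |
|---|---|---|---|---|---|---|
| 0 | 50% | 25% | 25 | 11.7 | 60% | 60% |
| 10% | 55% | 32.5% | 22.5 | 12.1 | 51% | 56% |
| 20% | 60% | 40% | 20 | 12.2 | 43% | 52% |
| 30% | 65% | 47.5% | 17.5 | 12.2 | 36% | 48% |

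The SE is √[(a(1 − a) + b(1 − b))/32] for reported rates a and b; at q = 0 it is √[(0.25 + 0.1875)/32] = 0.117. Power uses the normal approximation, one-sided 0.05, with 27 per arm for all mITT and 27(1 − q) per arm for the restricted set. Restriction does not lose power here: the difference stays at 25 points, which more than offsets the smaller denominator.

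If only 90% of the low-baseline group is still at 10 or below at a visit, equally in both arms, the rates move (58% v 38% at q = 20%) but the differences do not.

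**Response.** Staying still is not enough; the score must halve. A move from 2 to 1 qualifies, from 4 the requirement is 2 points, and at 0 the percentage is undefined. The SAP gives no rule for that case.

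**The case against.** The strongest objection is that the affected group may be nearly empty. No baseline MADRS distribution is given, and participants enter with severe PTSD: mean baseline CAPS-5 was 47.8 in Part A (Protocol 2.4.1). A reader might infer from the figure of about half in Protocol 2.1.1 that many participants start at 10 or below. The documents do not support that, because lacking a diagnosis of major depression is not the same as a MADRS of 10 or below, and excluding other primary diagnoses leaves comorbid depression in. This objection stands as a limit on size, which is why q starts at zero.

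Three other stronger readings do not hold.

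- *That the rule favours methylone.* With equal shares in the arms it pulls the difference toward zero.
- *That chance imbalance in the low-baseline group would appear as a treatment effect.* With 32 per arm the SD of the imbalance in composition is √[2q(1 − q)/32], or 7.5, 10 and 11.5 points at 10%, 20% and 30%. It reaches the remission difference only after multiplication by 1 − p in each arm, here 0.50 and 0.75. Most of it is ordinary sampling variation: the total SE moves only from 11.7 to between 12.1 and 12.2 points.
- *That low-baseline participants become 50% responders automatically.* They do not, as shown above.

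It is also fair to say that SAP 8.3.2.2.2 promises only a summary percentage. SAP 8.3.2.2.10 and 8.3.2.2.11 name the CMH test for PGI-C and CGI-I, so whether the general rule in SAP 8.3.1.2 reaches these measures is open. Absolute MADRS scores are summarized by visit and all efficacy data are listed, so low baselines would not be hidden. The table shells are in a separate file (SAP 11.2), and a restricted denominator there cannot be ruled out. None of this changes the definition in the SAP text, which misclassifies anyone who starts and stays at 10 or below.

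**Conclusion.** The point holds as a defect of definition in two secondary measures. Its size is conditional. If a share q starts and stays at 10 or below in both arms, remission is overstated in each arm and the difference is multiplied by 1 − q: nothing at q = 0, and 25 points reduced to 17.5 at q = 30%. Both q and the 50% v 25% are assumptions. For response, the defect is confined to very small baselines and the missing rule for a baseline of 0.

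The CAPS-5 primary endpoint is untouched. So is the MADRS MMRM, which analyses change with baseline as a covariate. The study is described as not confirmatory (SAP 8.1.5). This is a worthwhile and inexpensive correction, not a threat to the trial's main result.

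**What to change.** In SAP 8.3.2.2.2, report MADRS remission and response among mITT participants with baseline MADRS above 10, and show the denominator in each arm. This also disposes of the baseline-0 case. Add the number per arm with baseline MADRS of 10 or below to the baseline characteristics in SAP 8.2.3.2, which do not currently include it. Keep the MADRS MMRM in all mITT participants, so that anyone with a low baseline who worsens is still analysed. If an all-participant percentage is kept, label it *MADRS score of 10 or below*, not remission.

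The cost is SAP wording and one subset flag; MADRS is already collected at the Baseline visit (Protocol 1.3). The downside is a smaller denominator and a lower absolute remission rate in these summaries. The restriction is also not a complete remedy, since a move from 11 to 10 still counts as remission.
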